6.6 Supportive Care

All supportive measures consistent with optimal patient care may be given throughout the study. Patients should receive full supportive care, including transfusions of blood and blood products, antibiotics, antiemetics, etc., when appropriate. The reason(s) for treatment, dosage, and the dates of treatment should be recorded. GCSFs may be used for the management of treatment-emergent neutropenia at the investigator's discretion and according to the current American Society of Clinical Oncology (ASCO) guidelines. The use of hematopoietic growth factors is at the discretion of the treating physician and according to local institutional standards. For example: study participants who enter the study on stable doses of erythropoietin or darbepoetin may continue this treatment, and patients may start either drug during the study at the discretion of the treating physician.

6.7 Concomitant Medications and Therapies

All administered concomitant medications (including herbal supplements) and non-medicinal therapies (including transfusions) used 28 days prior to Cycle One Day One, and until 30 days after the last dose of study therapy will be recorded in the subject's research chart and corresponding eCRF. All medications, including those used to treat adverse events, chronic conditions or diseases, or as supportive therapy should be documented in the eCRF.

Allowed Therapy

Loperamide: For symptoms of diarrhea and/or abdominal cramping that occur at any time during a treatment cycle with cetuximab, patients will be instructed to begin taking loperamide. Loperamide should be started at the earliest sign of (1) a poorly formed or loose stool or (2) the occurrence of 1 to 2 more bowel movements than usual in 1 day or (3) an increase in stool volume or liquidity. Loperamide should be taken in the following manner: 4 mg at the first onset of diarrhea, then 2 mg every 2 hours around the clock until diarrhea-free for at least 12 hours. Patients may take loperamide 4 mg every 4 hours during the night. The maximum daily dose of loperamide is 16 mg/day. Patients should be provided with loperamide at the initial treatment visit so that they have sufficient supply on hand in case antidiarrheal support is required. Additional antidiarrheal measures may be used at the discretion of the treating physician. Patients should be instructed to increase fluid intake to help maintain fluid and electrolyte balance during episodes of diarrhea.

Antiemetics: Patients should receive antiemetics before cetuximab according to the treating physician and institutional guidelines.

Ancillary Therapy

Hormonal/Other Chemotherapeutic Agents: Treatment with hormones or other chemotherapeutic agents may not be administered except for steroids given for adrenal failure; hormones administered for non-disease-related conditions (e.g., insulin for diabetes); and intermittent use of dexamethasone as an antiemetic.

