6 STUDY INTERVENTION

6.1 Administration Schedule

The treatment plan includes single agent cetuximab. Cetuximab will be administered every 2 weeks (14 days). The initial dose of 500 mg/m² is to be administered by IV infusion over 120 minutes. Each cycle will be defined as 14 days of treatment.

Sites should make every effort to target infusion timing to be as close to 120 minutes as possible. However, given the variability of infusion pumps from site to site, a window of -5 minutes and +10 minutes is permitted (i.e., infusion time is 120 minutes: -5 min / +10 min).

In an effort to prevent a hypersensitivity reaction, all patients should be premedicated with

diphenhydramine hydrochloride 50 mg (or an equivalent antihistamine) by IV given approximately 30-60 minutes prior to the first dose of cetuximab. Premedication may be administered prior to subsequent doses, but at the Investigator's discretion, the dose of diphenhydramine (or a similar agent) may be reduced.

Patients should be closely monitored for treatment-related adverse events, especially hypersensitivity reactions, during the infusion and the post-infusion observation hour. For the duration that patients are on protocol therapy, adverse event monitoring will be done continuously. Patients will be evaluated for adverse events at each visit and are to be instructed to call their physician to report any clinically significant adverse events between visits.

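### If diarrhea persists, the loperamide schedule in section 6.7 passes the 16 mg/day maximum in the same paragraph, and patients are not told to stop at it

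*Combined protocol and SAP*

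**What the plan says.** The loperamide paragraph under Allowed Therapy in section 6.7 contains everything at issue:

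- **Schedule:** "4 mg at the first onset of diarrhea, then 2 mg every 2 hours around the clock until diarrhea-free for at least 12 hours".
- **Night option:** "Patients may take loperamide 4 mg every 4 hours during the night".
- **Limit:** "The maximum daily dose of loperamide is 16 mg/day". This comes directly after the night option and carries no condition.
- **Who takes it, and when:** at the earliest sign of loose or more frequent stools, "patients will be instructed to begin taking loperamide". On supply: "Patients should be provided with loperamide at the initial treatment visit so that they have sufficient supply on hand".
- **Further treatment:** "Additional antidiarrheal measures may be used at the discretion of the treating physician".

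Two other sections bear on it. Section 6.6 says "All supportive measures consistent with optimal patient care may be given throughout the study". Section 6.1 says patients are to be "instructed to call their physician to report any clinically significant adverse events between visits".

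No sentence says what a patient should do on reaching 16 mg while diarrhea continues, and the day over which the 16 mg is counted is not defined.

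**The concern.** The schedule tells the patient to keep dosing day and night until 12 hours have passed without diarrhea. The limit tells the patient not to go above 16 mg in a day. At 2 mg every 2 hours the schedule runs at 1 mg per hour, or 24 mg over a full day, so it cannot be kept up for a day within the limit.

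This matters because patients take the drug themselves at home, from a supply handed out in advance, starting at the first sign of diarrhea. Section 6.5 makes no cetuximab dose change for diarrhea, so its management rests on supportive treatment. Whoever writes the patient instructions from this paragraph has to decide which of the two statements gives way. What is at stake is a dosing instruction that, followed as written through a persisting episode, exceeds the protocol's own limit. No efficacy or design quantity is involved.

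**Working it through.** **Inputs, all from the loperamide paragraph of section 6.7.** First dose 4 mg at hour 0; 2 mg at hours 2, 4, 6 and so on; stop after 12 hours without diarrhea; night option 4 mg every 4 hours; limit 16 mg/day. The limit is stated rather than derived, so there is no calculation of the plan's to reproduce. The check is whether the schedule stays within it.

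**Running total from onset.** The total after the dose at hour h (h even) is 4 + 2 × (h/2) = 4 + h mg.

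- Hour 10: 4 + 10 = 14 mg
- Hour 12: 4 + 12 = 16 mg, exactly at the limit
- Hour 14: 4 + 14 = 18 mg, the first dose over it
- Hour 22 (last dose in the first 24 hours): 4 + 22 = 26 mg

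So the first 24 hours hold 12 doses, 4 + 11 × 2 = 26 mg. That is 10 mg above the limit (10/16 = 62.5%). Seven of the 12 doses fit within 16 mg and five do not.

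**A later full 24 hours of dosing.** 12 × 2 = 24 mg, which is 8 mg above the limit (8/16 = 50%). Eight doses fit and four do not.

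**Night option.** 4 mg every 4 hours is again 1 mg per hour. With an assumed 8-hour night, a later day totals (8/4) × 4 + (16/2) × 2 = 8 + 16 = 24 mg, the same as without the option. On the first day the total is 26 or 28 mg, depending on when the night falls. The option gives no relief from the limit.

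**When each dose falls due.** Dosing stops 12 hours after the last loose stool, so a dose at hour h is due only if the last loose stool comes later than hour h − 12.

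- One loose stool at onset: doses at hours 0 to 10, 14 mg, or 16 mg if the hour-12 dose is also taken. Within the limit.
- Hour-14 dose (first over the limit): last loose stool more than 14 − 12 = 2 hours after onset.
- Hour-22 dose (full 26 mg): more than 22 − 12 = 10 hours after onset.
- Hour-46 dose (full 24 mg in hours 24 to 46): more than 46 − 12 = 34 hours after onset.

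**If the day is a calendar day.** For onset before 10:00 the first dose over the limit is still the hour-14 dose. For onset from 10:00 to midnight the count restarts before 16 mg is exceeded. The breach then comes at the ninth dose of the second calendar day, between hour 18 (onset from 22:00) and hour 30 (onset 10:00 to 11:59). By the same rule those doses need a last loose stool more than 6 to 18 hours after onset. The definition of the day therefore changes when the limit is passed. In an episode that persists long enough, it is passed under either definition.

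**The case against.** The strongest reply is that there is no true contradiction. The maximum is unconditional and comes immediately after the doses it limits. Ordinarily a stated maximum is a ceiling on what precedes it: dose every 2 hours and stop at 16 mg. That is very probably the intent, and this part of the reply stands. A reader might infer that the protocol leaves the maximum without force, or directs patients to take 26 mg a day. The documents do not support either reading. What is missing is narrower: an instruction to stop at the limit, in a paragraph whose only stated stopping point is 12 diarrhea-free hours.

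A second reply is that many episodes never reach the limit. This also stands, and the totals above hold only under the durations shown.

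A third is that safeguards exist: extra antidiarrheal measures at the physician's discretion, full supportive care under section 6.6, and the instruction in section 6.1 to call about clinically significant events. These reduce the chance of prolonged unsupervised dosing. None of them is linked to reaching 16 mg, so they soften the gap without closing it.

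**Conclusion.** The point holds as a minor inconsistency in a patient dosing instruction. Under persisting diarrhea the schedule passes the stated maximum at hour 14 from onset on a rolling count. It exceeds the maximum by 10 mg in the first 24 hours and by 8 mg on a later full day of dosing. These figures assume that doses are taken exactly on schedule and that loose stools last as long as each total requires.

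A reader might go further and estimate how many participants would exceed the limit. Section 3.2.4 gives a diarrhea rate of 28%, which in 25 patients would be 0.28 × 25 = 7. That counts patients with any diarrhea. The documents give no episode durations, so the number who would pass 16 mg cannot be derived. Nor do they describe any harm from exceeding 16 mg beyond stating the maximum. The patient-facing instructions are not in the documents, so what patients are actually told is unknown. Eligibility, endpoints, sample size and analysis are unaffected.

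**What to change.** Add to the loperamide paragraph of section 6.7 that:

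1. the 16 mg/day maximum applies to both the every-2-hours and the night-time schedules;
2. dosing stops once 16 mg has been taken that day, with the day defined by the sponsor (any 24 hours is one option, and avoids dependence on the time of onset);
3. a patient who still has diarrhea at that point should call the physician about the additional antidiarrheal measures the paragraph already allows.

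Use the same wording in any patient instructions. The cost is a sentence or two of text in a protocol amendment, with nothing to change in the design or analysis.

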6.7.1 Radiotherapy

If deemed necessary by the treating investigator, palliative radiation therapy for a single site of bone or brain metastasis is allowed. The radiation field must not affect any of the target lesions designated for disease assessment. Protocol treatment will be held during radiation therapy and will be re-started 2 weeks following the conclusion of therapy.

6.7.2 Prohibited Therapy

Medications or vaccinations specifically prohibited in the exclusion criteria are not allowed during the active treatment period. Subjects are prohibited from receiving the following therapies during the treatment phase of this trial:

- Anti-cancer systemic chemotherapy or biological therapy;
- Other investigational agents;
- Radiation therapy (with the exception noted above);
- Any live-attenuated vaccine therapies for the prevention of infectious disease (e.g. MMR, or rotavirus); COVID-19 vaccines are allowed.

If a subject requires treatment with one or more of the listed prohibited medications, the subject may need to be taken off study therapy. Each case will be considered and if possible, the investigator should discuss with the DSMC and Medical Monitor prior to initiating prohibited therapy.

6.8 Duration of Therapy

Subjects will receive study treatment until treatment discontinuation criteria is met. Upon meeting treatment discontinuation criteria, subjects will continue on the study in follow-up until study discontinuation criteria are met.

6.8.2 Criteria for the Discontinuation of Study (“Off Study”)

Subjects will be taken off study for the following:

- Completed study follow-up period;
- Participant or legally authorized representative requests to be fully withdrawn from the study;
- If, in the investigator's opinion, the continuation of the trial would be harmful to the subject's well-being;
- The subject is lost to follow-up;
- Screen failure;
- Death.

6.8.3 Withdrawal of consent

Subjects are free to withdraw from the study at any time without prejudice to further treatment. Subjects who withdraw consent for further participation in the study will not receive any further study medications or further study observation.

If a subject withdraws consent, they will be specifically asked if they are withdrawing consent to all further participation in the study including any further follow-up (e.g., survival contact telephone calls). Survival status may be obtained from public records for subjects who have withdrawn from any further follow-up contact.

6.8.4 Long Term Follow-Up

Upon discontinuation of study therapy, subjects will be followed for survival and the initiation of subsequent anticancer therapy from the date of study therapy initiation until death, end of the study, or subject withdrawal of consent, whichever comes first. Subjects or their legally

authorized representatives will be contacted every three months (± 14 days) from end of study treatment until death, end of the study, or subject withdrawal of consent, whichever comes first. Survival and subsequent treatment status may be collected by public records, medical records, or by contacting the subject or their legally authorized representative by phone. All efforts should be made to contact the subject at these time points. Refer below for Lost to Follow-Up guidelines.

6.8.5 Lost to Follow-Up

Subjects will be considered lost to follow-up only if no contact has been established by the time the study is completed, such that there is insufficient information to determine the subject's status at that time. Subjects who refuse to continue participation in the study, including telephone contact, should be documented as "withdrawal of consent" rather than "lost to follow-up." Investigators should document attempts to re-establish contact with missing subjects throughout the study period. If contact with a missing subject is re-established, the subject should not be considered lost to follow-up and evaluations should resume according to the protocol.

When a subject is lost to follow-up, site personnel should check hospital records, the subjects' current physician, and a publicly available death registry to obtain a current survival status.

In the event that the subject has actively withdrawn consent, the survival status of the subject can be obtained by site personnel from publicly available death.

7 STUDY ASSESSMENTS

Every effort should be made to ensure that the protocol-required tests and procedures are completed as described. However, it is anticipated that there may be circumstances, outside of the control of the Investigator that may make it unfeasible to perform the test. In these cases, the Investigator will take all steps necessary to ensure the safety and well-being of the subject. When a protocol-required test cannot be performed, the Investigator will document the reason for this and any corrective and preventive actions that he or she has taken to ensure that normal processes are adhered to as soon as possible.

7.1 General Assessments

7.1.1 Participant Consent

Before the initiation of any study procedures, all potential subjects or their legal representative must be fully informed of the risks and potential benefits of trial participation and demonstrate understanding. An informed consent document must be signed and dated by the participant or their legal representative indicating that they understand the risks and consent to participation and treatment on the study. The Principal Investigator or their appropriately trained and delegated study personnel conducting the informed consent discussion must also sign and date the document. A copy of the signed document should be provided to the subject.

Procedures, laboratory tests, or imaging performed as part of the standard of care prior to subject consent may contribute to the assessment of eligibility and/or screening procedures if performed during the screening period.

7.1.2 Medical History

The investigator or appropriately trained and delegated study personnel will collect medical history to the extent that supports the assessment of eligibility. The medical history will include any active conditions and any conditions deemed to be clinically significant by the treating investigator. The use of symptom terms should be discouraged; if possible, terms describing the principal condition or syndrome should be used.

When collecting medical history specific attention should be given to:

- Prior history of cancer, family history of cancer
- History of Coronary Artery Disease
- Alcohol history (never used alcohol, current alcohol user, former alcohol user)
- Smoking history (never smoked, current smoker, former smoker)
- Pack years (average number of packs per day and number of years smoked)
- Current employment status (employed, retired, student, unknown, other)
- Insurance status (private insurance, Medicare, Medicaid, VA, military, not insured, self-pay, unknown, other)

7.1.3 Cancer History

The oncologic history of the malignancy under study will be collected at the screening visit and will include prior regimens (duration of therapy, the best response on therapy, date of discontinuation, and reason for discontinuation), surgery, radiation therapy, and sequence. The details of genomic sequencing, site of metastases will be collected.

7.1.4 Concomitant Medications

All medications currently being used by a study participant, regularly or as needed, must be reviewed and documented by the investigator or qualified designee. Specific attention should be given to medications with a protocol required washout as described in the exclusion criteria and any medication taken 28 days prior to cycle one day one. Refer to Section 6.7.2 for prohibited medications.

During protocol therapy, any medications taken by the patient or used to treat an adverse event will be documented in the subject's research chart and the corresponding eCRF. If a new anticancer therapy is initiated during study follow-up, the new therapy should also be recorded in the subject's research chart and corresponding eCRF.

7.1.5 Tumor Mutation Testing

It is required that all subjects have histological confirmation and documentation of APC, TP53, RAS mutation through local laboratory testing. The mutational status must be confirmed by a Clinical Laboratory Improvement Amendments (CLIA) approved test using either tumor tissue or ctDNA done as part of standard of care testing. Additionally as part of exploratory aim, the blood based cell free DNA assay to test for APC, TP53, KRAS, NRAS, HRAS, BRAF will be assessed every 8 weeks coinciding with CT imaging. The cell free DNA assay is performed using

ultrasensitive duplex sequencing assay at Intermountain Precision Genomics. The duplex sequencing results have a mean duplex depth >22,000x per replicate; and peak duplex depth >35,000x per replicate.

7.2 Safety Assessments

7.2.1 Physical Examinations and Vital Signs

Subjects will have physical examinations to include major body systems, vital signs (blood pressure, heart rate, respiration rate, pulse oximetry, and body temperature), assessment of ECOG performance status (see Appendix 1), weight, and height (height will be measured at screening only) at the time points described in the Schedule of Events. If necessary to facilitate scheduling, the physical exam may occur one day before study treatment.

7.2.2 Adverse Events

Adverse events experienced during trial participation will be collected per the Schedule of Events and Adverse Events Section. Each study participant will be questioned about the occurrence of adverse events in a non-leading manner. Should the treating investigator feel that the adverse event is attributed to study therapy, dose modification guidelines in the Dose Modification Section will be followed.

7.2.3 Laboratory Assessments

Samples for all laboratory assessments will be drawn at the time points indicated in the Study Calendar and when clinically indicated. Laboratory tests may be performed up to 3 days before the scheduled clinic visit. All safety laboratory analyses will be performed by the local laboratory for each study center. When applicable, all safety laboratory assessments must be reviewed by the treating investigator before study drug administration. When applicable, results from the pregnancy test must also be available for review before dosing.

Table 3 : Laboratory Assessments

Laboratory Assessments	
Complete Blood Count with Platelet Count and Differential	
 • White Blood Cell Count • Hemoglobin • Platelets • Absolute Neutrophil Count • Absolute Lymphocytes
Chemistry	
 • Complete Metabolic Panel 
 ○ Sodium ○ Potassium ○ Chloride ○ Carbon Dioxide ○ Alkaline Phosphatase ○ Aspartate Aminotransferase ○ Alanine Aminotransferase ○ Urea Nitrogen

	
  Glucose  Creatinine  Calcium  Protein  Albumin  Bilirubin • Magnesium level
Pregnancy	
 • Beta-hCG Qualitative Serum
Tumor Marker	
 • CEA
Bloodmarker	
 • CfDNA

7.3 Efficacy Assessments

7.3.1 Disease Assessment

Disease assessments must include all known or suspected sites of disease; therefore, the decision for body areas to be scanned will depend on the extent of disease. The minimum recommended body areas to be scanned is chest, abdomen, and pelvis. Response will be defined by RECIST 1.1 (Appendix 3).

Disease assessments will be evaluated radiologically and conducted at baseline (within 28 days before the first dose of study treatment) and then every 8 weeks thereafter regardless of dose holds or delays. Disease assessments will continue until disease progression. Subjects who discontinue treatment for reasons other than progression will continue to have disease assessments until documented clinical or radiographic progression or initiation of subsequent therapy. In addition, radiological tumor assessments will be conducted whenever disease progression is suspected (e.g. symptomatic deterioration) or when clinically indicated. The schedule of tumor assessments should be fixed according to the calendar, starting with cycle one day one, regardless of treatment delays or interruptions due to toxicity.

Brain CT or MRI scans are required at baseline for all subjects with stable brain lesions and for those for whom Central Nervous System (CNS) involvement is suspected. If stable brain metastases are present at baseline, brain imaging should be repeated at each tumor assessment. Otherwise, brain imaging will be conducted post-baseline only when clinically indicated.

The CT and MRI scans should be performed with contrast agents unless contraindicated for medical reasons. Consistent imaging modality should be used for all disease assessments.

7.3.1.1 *Photography of Cutaneous Lesions*

Cutaneous lesions not evaluable by CT or MRI will be documented by color digital photography, including a ruler to estimate lesion size. Photographs must be taken in a manner that protects subject identity and confidentiality (e.g. covering eyes or defining marks or characteristics). Cutaneous lesions may be considered target lesions if they meet RECIST v1.1 criteria, otherwise they may be considered non-target lesions. Photographs of cutaneous lesions will be taken at screening and on the same day as a tumor assessment visit, or at the first clinic visit following each tumor assessment

